8.3.3. Clinical Lab assessments related to VL evolution

Hematology parameters are commonly affected in a patient with VL. At baseline, the patient is likely to present anemia, low WBC and possibly low platelets.

Exclusion criteria are defined as not to include in the clinical trial patients with severe anemia (Hb< 5g/dL). In addition, Hb level, platelets and WBC counts will be assessed by the investigator together with the clinical presentation and other laboratory parameters to judge if patient has signs of severe VL disease, requiring AmBisome therapy.

Hematology parameters must be recorded at screening, D3, D7, D14, D28, D56 and D210. It is expected that the hematological parameters recover with time after treatment.

Albumin will also be assessed before and after treatment, at screening, Day 28 and Day 210.

Confidential Page 42 of 68

8.3.4. Post-kala-azar dermal leishmaniasis (PKDL)

Patients will be monitored closely for post-kala-azar dermal leishmaniasis (PKDL) through the course of the study. Diagnosis will be made clinically based on the typical appearance and distribution of the rash. Presence of PKDL will be assessed at screening, on day 28 and during follow-up assessments on day 56 and day 210.

Grading will be noted during the assessment times as follows:

- Mild (Grade 1): lesions mainly on the face and head, with others scattered on arms, chest and back
- Moderate (Grade 2): the upper part of the chest and arms are also affected
- Severe (Grade 3): lesions may be found on the whole body.

Patients who develop severe PKDL (grade 3) or have mucosal and/or eye involvement (any grade) will require treatment with rescue medication at the discretion of the attending physician.

8.4. Pharmacokinetics and Pharmacodynamics Assessments

8.4.1. Pharmacokinetic Assessments

Patients in arm 1 will have pharmacokinetics measurement of MF at D14, whereas all patients in arm 1 and 2 will have PK measurement of MF at D28 and D56 in order to verify adherence to the treatment.

In addition, intensive sampling for both PM and MF PK will be performed in a subset of patients defined as the intensive cohort: originally 40 in each MF/PM combination arms, with selection of 20 pediatric (≤12 yrs) patients and 20 adolescent/adult patients (>12 to ≤50 yrs). Because arm 2 is discontinued, the number of patients enrolled in this arm in the PK/PD intensive cohort will most probably not reach 40, however samples collected will still be analysed. Enrollment in this intensive cohort will be limited to specific sites located in Sudan and Kenya and as far as possible should be balanced between the two countries. MSF sites will not participate to the enrollment in the intensive PK/PD cohort. These sites will be selected based on their experience, equipment and resources available. Since previous trials (LEAP0714 and LEAP0208) have raised questions on both the (reduced) absorption rate, but also extent of absorption (bioavailability), of MF in East African VL patients, denser sampling is required in this trial than previously performed for MF pharmacokinetics. Due to the PK nonlinearities observed in pediatric patients receiving the allometric MF dosing (LEAP0714), the inclusion of children in this PK sub-study is important and therefore the aim is to have equal numbers of patients below 12 years and above 12 years included in the PK sub-study, to allow for comparison. For PM, we have included a sparse sampling scheme to enable assessment of pharmacokinetic profiles, with subsequent use of population PK modelling to analyze the data. PM PK will be assessed on both day 1 and day 14 of treatment to assess the influence of changing patient characteristics during the treatment period (e.g. increasing body weight, reduced liver damage, etc.) on the PK of PM and to assess potential accumulation of the drug during the treatment period.

Confidential Page 43 of 68

In order to avoid multiple blood sampling in young children, only children from 7 years of age and weighing more than 20 kg will be included in the PK intensive cohort.

To reduce the number of total samples/blood volume per patient in the intensive cohort, a mixed sampling approach will be performed. Patients will be randomly allocated to sparse sampling schemes to allow for a pooled PK analysis.

As much as possible, a single blood draw should be performed per study visit to avoid multiple vein punctures. Sample for both MF and PM PK will be in general a 2mL EDTA whole blood sample/time point. For time-points where only MF PK is to be assessed, also 2 ml EDTA whole blood sample/time point will be collected to accommodate with the lowest volumes of tubes currently available on the market.

The pharmacokinetics of both PM and MF will be determined using validated liquid chromatography—tandem mass spectrometry (LC-MS/MS) bioanalytical assays (PM to be validated). The pharmacokinetics of both drugs will be determined in plasma, unless a dried-blood-spot method is developed for PM prior to initiation of this trial.

Samples will be stored on site at minimally -20°C and regularly shipped under frozen conditions to the respective capitals for shipment to Amsterdam, the Netherlands. Samples will be analysed for their MF/PM content at the Bioanalytical Laboratory at the Netherlands Cancer Institute — Antoni van Leeuwenhoek Hospital, following a validated procedure using liquid chromatography coupled to tandem mass spectrometry (LC-MS/MS). The development and validation of the assay for MF has previously been published (Dorlo et al., 2008). A bioanalytical assay for paromomycin in human plasma has been described in literature previously and will be validated during the progressing review period and implementation of this protocol.

8.4.1.1. Paromomycin pharmacokinetic assessments

PM PK assessments will be performed only in the intensive cohort (subset of 40 patients in each MF/PM combination arms) at Screening, D1 and D14. The screening sample can be collected at any day during screening period. PM PK sample at D1 and D14 will be collected at 0, 1, 2, 4, 8, 24 hrs post-dose.

In order to minimize blood volume collected, each patient will be randomly allocated to one of the following sparse PK sampling schedules:

- D1: either 1, 2, 4, 24h or 1, 2, 8, 24h.
- D14 (arm 1 and 2): either 0, 1, 2, 4, 24h or 0, 1, 2, 8, 24h.

Time of drug administration and time of PK samples collection have to be recorded systematically.

8.4.1.2. Miltefosine pharmacokinetic assessments

MF PK assessments will be performed at D14 for subjects in arm 1 and at D28 and D56 for all subjects in arm 1 and 2 to confirm adherence to treatment. Subjects who consent to participate to the intensive cohort will have MF PK assessments performed at Screening, D1, D7, D14, D28 and D56 in both arms and an additional assessment

Confidential Page 44 of 68

used to be done at D21 in arm 2 only (not applicable anymore in this protocol version). The screening sample can be collected at any day during screening period or before the administration of the 1st dose at D1.

In the intensive cohort, MF PK sample at D1 and D14 will be collected at the same time points as PM PK at 0, 1, 2, 4, 8 and 24h (according to the sparse sampling scheme the patient is allocated to). The 8h MF PK sample will be collected always before the 2nd daily dose. D7 and D21 (arm 2 only, not applicable in this protocol version) PK samples will be collected prior to the morning dose. D28 PK sample used to be collected prior to the morning dose in patients allocated to arm 2 and will be collected in the morning in patients allocated to arm 1. In the follow-up period (D56), PK sample shall be collected in the morning. Time of drug administration and time of PK samples collection have to be recorded systematically.

8.4.2. Pharmacodynamic Assessments

Parasite load in blood and tissue aspirate (bone marrow or spleen): PD assessment will be based on real time quantitative polymerase chain reaction (qPCR) for *L. donovani* in EDTA blood or tissue aspirate, based on the amplification of kinetoplastid DNA (kDNA) (other *Leishmania* DNA targets may also be considered), to assess the parasite clearance over time during the treatment with two combination regimen of PM and MF or treatment with SSG/PM.

All patients will have qPCR in tissue and blood at screening and at Day 28 assessment; and during follow-up if there is suspicious of relapse.

In addition, the patients (40 in arm 1 and probably fewer patients in arm 2 now this arm is discontinued) in the intensive cohort who consent to have multiple sampling for PK will also have qPCR blood samples collected at D0, 3, 7, 14, 28, 56 and 210.

Approximately 1 ml EDTA whole blood will be immediately separated from blood EDTA samples taken (e.g. for Complete Blood Count or PK analysis) for the qPCR analysis. The blood samples and also the remainder of bone marrow/spleen aspirate sample (optional) will be immediately diluted with DNA stabilizing buffer solution (L6 buffer) and can then be stored up to 2 years at frozen temperature.

Furthermore, additional relevant PD markers will be considered for analysis in order to monitor treatment effect.

8.5. Assessment of Safety

Safety of the different treatment regimens will be assessed through routine monitoring of adverse events. At each study visit, the patients will be enquired about current adverse events or any events observed during the period previous to the visit. In addition, evaluation of hematology and blood chemistry parameters, regular measurement of vital signs and physical examinations will be made at scheduled follow-up visit.

Audiometric test will be performed at baseline and on days 14, 28 and 210 for all patients.

ECG will be performed at baseline and on day 14 in all arms, and in addition on days

Confidential Page 45 of 68

7 and 28 in the reference arm SSG/PM. SOPs will be developed to guide investigators on audiometry and ECG assessments.

Urine pregnancy tests will be performed in woman of child-bearing potential at baseline to exclude any pregnancy, and on D28, D56 and D210 visits to monitor eventual unexpected pregnancy.

HIV test will be repeated at the D210 visit only for patients in Gondar and Abdurafi sites, due to high prevalence of HIV/VL co-infected patients (15%) in this specific population.

The frequency and severity of AEs will be described, as well as frequency of SAEs or AEs that lead to treatment discontinuation. See section 8.6 for AE definition and reporting.

8.5.1. Laboratory examinations

Hematology parameters hemoglobin, WBC with differential and platelets will be analyzed at screening, on days 3, 7, 14, 28, 56 and 210.

Biochemistry parameters ALT, AST, TBIL and CRE will be analyzed at screening, on days 3, 7, 14 and 28.

Samples will be analyzed at the local laboratory using standardized equipment.

Approximately 3 ml of blood will be collected at each visit: 1 ml in EDTA for the hematology and 2 ml in dried tube for the biochemistry.

Lab parameters abnormal values will be assessed for clinical significance and will be graded according to CTCAE v4.03 (see section 8.6.7).

8.6. Adverse event definitions and reporting

8.6.1. Adverse Event definition

Any untoward medical occurrence in a clinical trial subject administered a medicinal product and which does not necessarily have a causal relationship with this treatment.

It can therefore be any unfavourable and unintended sign (e.g. an abnormal laboratory finding), symptom, or disease temporally associated with the use of a medicinal product, whether or not considered related to the medicinal product.

Definition of an AE includes worsening (in severity and frequency) of pre-existing conditions ("Medical history") before first Investigational Medicinal Product (IMP) administration and abnormalities of procedures (i.e. ECG, X-ray...) or laboratory results which are assessed as "clinically significant" (see details in section 8.6.2).

What is not an AE?

Confidential Page 46 of 68

- Medical conditions present at the initial study visit that do not worsen in severity or frequency during the study are NOT considered as AE.
- Symptoms, exacerbation or worsening of the studied disease will NOT to be considered as AE nor captured on the AE page of the CRF if consistent with the anticipated natural progression of the disease (overall and for this given subject).
- Lack of efficacy of the IMP is NOT considered as AE.

8.6.2. Assessment of laboratory abnormalities

For every laboratory assessment, the investigator will evaluate if the lab test is normal or abnormal. If abnormal, the investigator will assess if this finding is clinically significant or not. If a lab parameter is abnormal and clinically significant, it should be reported as an adverse event (AE).

An abnormal lab test must be compared with the previous value.

An AE is a new event after the administration of the 1st dose of the study drug or a worsening in the condition (in the case of lab tests, increase in severity by CTCAE v4.03) which is judged clinically significant by the investigator.

Laboratory abnormalities should be assessed as "clinically significant" (and therefore have to be reported as an AE) only if they meet AT LEAST ONE of the following conditions:

- The abnormality suggests a disease and/or organ toxicity AND this abnormality was not present at the screening visit or is assessed as having evolved since the screening visit
- The abnormality results in discontinuation of the study drug
- The abnormality requires medical intervention or concomitant therapy

Lab parameters which are classified with regards of severity as CTCAE v4.03 Grade 3 or Grade 4 must be carefully assessed, as they are likely to require medical intervention and/or be life-threatening in terms of severity.

For the purpose of this protocol, all clinically significant Grade 3 and Grade 4 lab abnormalities must be reported as an AE.

When reporting an abnormal lab, a clinical diagnosis should be recorded rather than the abnormal value itself, if available (for example, "hypokalemia" rather than "decreased potassium levels"). Furthermore, lab abnormalities which present with clinical signs and symptoms will also be considered clinically significant. In these cases, again the adverse event should be recorded as the syndromic clinical diagnosis rather than clinical signs and symptoms (ex. acute pancreatitis instead of each finding separately; high levels of amylase, high levels of lipase, abdominal pain and vomiting).

For any abnormal clinically significant lab value, the investigator will carefully assess if the event is due to the natural disease progression (e.g. anaemia during the first days of treatment). If the abnormality is associated with the anticipated VL disease symptoms, it does not need to be reported as an AE, unless if it meets the criteria of a

Confidential Page 47 of 68

clinically significant event.

8.6.3. Serious Adverse Event

An adverse event will be defined as serious if it

- results in death,

i.e. causes or contributes to the death.

- is life-threatening,

in this context refers to an AE/Adverse Reaction (AR) in which the patient was at risk of death at the time of the AE/AR; it does not refer to an AE/AR that hypothetically might have caused death if more severe.

- requires in-patient hospitalisation or prolongation of existing hospitalisation,

i.e. the AE requires at least an overnight admission or prolongs a hospitalization beyond the expected length of stay.

In this protocol, the patient is expected to be hospitalized for 14 days, with discharge expected on D15. If the patient presents an AE that requires hospitalization for more than 24hs after D15, this event will be considered an SAE. However, if the patient remains hospitalized for social reasons, it will NOT be considered as an SAE.

Hospital admissions or prolongation of hospitalisation for surgery planned before study entry, for social reasons, for any elective surgery (i.e. plastic surgery) or for normal disease management (including treatment adjustment) are NOT to be considered as SAE according to this criterion (i.e. if the protocol or the standard management of the disease under study requires planned hospitalization).

results in persistent or significant disability or incapacity,

i.e. the AE resulted in a substantial disruption of the subject's ability to conduct normal activities.

is a congenital anomaly / birth defect,

i.e. an adverse event outcome in a child or foetus of a subject exposed to the Investigational Medicinal Product (or marketed medicinal product) before conception or during pregnancy.

- is an important medical event, i.e. is medically significant.

Medical and scientific judgment should be exercised in deciding whether other situations should be considered serious events/reactions, such as important medical events that might not be immediately life-threatening or result in death or hospitalization but might jeopardize the patient or might require intervention to prevent one of the other outcomes listed above.

Confidential Page 48 of 68

In addition, any suspected transmission via a medicinal product of an infectious agent is also considered a serious adverse event/reaction.

Note: **SAE onset date** is the SAE start date or date a pre-existing AE becomes serious.

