Patients are hospitalized for 14 days of PM and MF treatment for both arm 1 and arm 2. MF treatment starts at the same time as PM treatment and for arm 2 it used to continue on an out-patient basis until completion of the 28 days treatment.

During hospitalization, compliance to treatment is assured. During this period, patients or parent/guardian will be instructed on MF treatment, the daily dose (morning and afternoon), and the administration with food to avoid or minimize any vomiting. Patients in arm 2 were discharged after 14 days in hospital with clear instructions on how to continue MF treatment, and to return for the Day 28 visit. Compliance during the 14 days treatment outside the hospital was assessed by collecting the empty blisters pack at the day 28 visit and checking for any unused drug. A daily diary was provided to these patients in order to guide them in their treatment schedule at home. Any episode of vomiting reported by the patient was captured by the clinician at day 28 visit. In case of multiple episodes of vomiting or any other adverse events, patients were instructed to come to the hospital for an assessment and management in an unscheduled visit.

Compliance will be further assessed through cross-check with PK data.

SSG-PM combination therapy will be administered for 17 days according to routine VL

Confidential Page 24 of 68

treatment guidelines. Patients will remain hospitalized for the entire duration of SSG-PM treatment. Patients in all arms will come back for the end-of-treatment assessments visit at day 28.

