8.1. Timing of Assessments

Assessments will be carried out at Screening period (day -7 to 0) and on days 1, 3, 7, 14, 21, 28, 56 and 210. It will include clinical, parasitological, haematological, biochemistry, safety, pharmacokinetic and pharmacodynamics assessments.

A table with the schedule of events is listed under section 5.

All patients will be hospitalized for screening/baseline procedures until completion of day 14 (arm 1 and 2) and day 17 (arm 3) procedures (approximately 21-24 days). Day 28, 56 and 210 assessments will be conducted as outpatient visits.

Assessments performed during study visit at D28 will have allowable window of +1day, due to critical PK assessments at this EOT visit. Therefore, it is acceptable to have patients readmitted at the hospital the day before (D27). In the case of patients coming from very remotes areas, mobilization will be strengthened and it will be allowed to readmit those patients 2 to 3 days before D28 assessments.

All other assessments performed during treatment period (D1 until < D28) will have an allowable window of \pm 1 day. In the follow-up period, visit windows will be: day 56 (\pm 7 days) and day 210 (\pm 14 days).

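### The SAE prolongation rule assumes a D15 discharge for every patient, but arm 3 is planned in hospital through D17, so some arm 3 events can be counted as SAEs without prolonging the stay

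*Combined protocol and SAP*

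**What the plan says.** Section 8.6.3 makes an AE serious if it needs at least an overnight admission or "prolongs a hospitalization beyond the expected length of stay". It then fixes that stay without naming an arm: "In this protocol, the patient is expected to be hospitalized for 14 days, with discharge expected on D15". The working rule follows: "If the patient presents an AE that requires hospitalization for more than 24hs after D15, this event will be considered an SAE". The next paragraph of the section exempts admissions or longer stays that belong to normal disease management, including the case "if the protocol or the standard management of the disease under study requires planned hospitalization".

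The planned stay is not the same in every arm. Section 8.1 keeps patients in hospital "until completion of day 14 (arm 1 and 2) and day 17 (arm 3) procedures". Section 3.1 says of the reference arm: "Patients will remain hospitalized for the entire duration of SSG-PM treatment", which is 17 days. The protocol summary says the same. No arm 3 version of the D15 rule appears anywhere in the document.

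Section 2.2.2 lists SAE frequency as a secondary safety endpoint. Section 7.6 states that the trial is open label.

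**The concern.** A 14-day stay with discharge on D15 describes arms 1 and 2 but not arm 3. Applied literally, the D15 rule can make an arm 3 AE serious while the patient is still inside the stay that the protocol itself planned. The general criterion and the exemption in the same section point the other way. An investigator who follows the specific sentence reports an SAE, and one who follows the general criterion does not.

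Two things are at stake. One is consistent classification across sites, which matters because section 8.6.7 requires every SAE to be reported within 24 hours. The other is a possible over-count of SAEs in the reference arm, on a secondary safety endpoint, in a trial where the arm is known to whoever classifies the event.

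**Working it through.** No power or alpha figure bears on this point. The check is day arithmetic, followed by a comparison of the sentences.

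**1. Reproduce the plan's own figure for the stay.** Section 8.1 gives hospitalisation "until completion of day 14 (arm 1 and 2) and day 17 (arm 3) procedures (approximately 21-24 days"). Inputs: a screening period of up to 7 days (section 8.1), and in-patient treatment to day 14 (arms 1 and 2) or day 17 (arm 3).
- Arms 1 and 2: 7 + 14 = 21 days.
- Arm 3: 7 + 17 = 24 days.

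Both ends of the stated range are reproduced. The difference, 24 − 21 = 3 days, agrees with the reduction of at least 3 days that section 10.6 counts as an advantage of the test arm. The longer arm 3 stay is therefore intended.

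**2. Cut-off in section 8.6.3.** D15 + 24 hours = about D16, for every patient.

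**3. Planned discharge in arm 3.** There are two readings.
- Discharge once day 17 procedures are complete (section 8.1): D17.
- Section 8.6.3's own convention, where a 14-day stay means discharge on D15 (14 + 1): 17 + 1 = D18.

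**4. Cut-off against planned discharge.**

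| Arm | Planned discharge | Cut-off | Cut-off relative to planned discharge |
|---|---|---|---|
| 1 and 2 | D15 | D16 | 1 day after |
| 3, first reading | D17 | D16 | 1 day before |
| 3, second reading | D18 | D16 | 2 days before |

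In arms 1 and 2 the rule works as a 24-hour allowance after planned discharge. In arm 3 it takes effect 1 to 2 days before planned discharge.

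**5. One event under each sentence.** Take an arm 3 AE that starts on D14, is judged to require in-patient care, and resolves on D17 with discharge as planned.
- D15 rule: SAE, because in-patient care was required for more than 24 hours after D15.
- General criterion: not an SAE by prolongation, because the planned stay was not exceeded.
- Planned-stay exemption: arguably not an SAE, although the exemption does not say whether it covers an AE that itself needs in-patient care during a planned stay.

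One section therefore gives different answers for the same event.

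**6. Size.** The documents give no rate for AEs requiring in-patient care around D16 to D18, so the number of affected events cannot be computed. For scale, with 170 patients in arm 3 (section 4):
- 1 patient: 1/170 = 0.59 percentage points.
- 2 patients: 2/170 = 1.18 points.
- 5 patients: 5/170 = 2.94 points.

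The shift applies only to a patient who has no other SAE.

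**7. After an arm-specific correction.** Arms 1 and 2 keep the cut-off at D16. In arm 3 it becomes 17 + 1 = D18 or 18 + 1 = D19, which is 2 to 3 days later than now.

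**The case against.** The strongest reply has four parts.

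- **The trigger is narrow.** The rule needs an AE that requires hospitalisation. An arm 3 patient who is in bed on D16 or D17 to finish SSG-PM, with an AE that could be treated as an out-patient, does not meet it. This stands, and it limits the problem to AEs judged to need in-patient care in their own right.
- **Arm 1 is exposed to the same sentence.** An arm 1 patient kept in for an AE more than 24 hours past D15 is an SAE, and a discharged patient readmitted overnight is an SAE under the general criterion. On this view a common day is even-handed, and an arm-specific day would make the same AE on D17 serious in arm 1 but not in arm 3. This stands in part. It shows that the correction creates an asymmetry of its own, which the reporting must address. It does not rescue the present text, because the protocol's stated criterion is prolongation beyond the planned stay and not a common clock. In arm 1, staying past D15 reflects a decision not to discharge. In arm 3 no such decision has yet arisen, so the need for in-patient care is harder to judge. If a common clock is intended, the section must say so and reconcile the exemption.
- **The exemption already covers it.** It covers a stay that serves only to complete treatment. It does not clearly cover an AE needing in-patient care during that stay.
- **The consequences are limited.** Section 10.7 describes SAEs by arm; only frequent adverse drug reactions are compared and tested. Each SAE has a narrative, and section 8.6.7 records the seriousness criterion, so events that are serious only by prolongation can be found. This stands.

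**Conclusion.** The sentence is wrong as written for arm 3 and contradicts both its own section and section 8.1. The consequence is narrow: a possible over-count of arm 3 SAEs within a window of 1 to 2 days, and inconsistent classification between sites. This assumes that some investigators follow the D15 sentence and not the general criterion, and that AEs requiring in-patient care occur in the window and resolve by planned discharge. The number may be small. Each patient reclassified is worth 0.59 percentage points of the arm 3 SAE proportion.

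A reader might infer three stronger conclusions, none of which the documents support.
- **That the rule demonstrably biases the safety comparison towards MF/PM.** The direction is possible, but arm 1 patients kept in or readmitted for such an AE also count, and nothing shows that any affected arm 3 event exists.
- **That the over-count can be sized.** Assuming that 3–10% of arm 3 patients have an AE being managed on those days gives 5–17 of 170. No rate in the documents supports that range, and AEs merely being managed in hospital are a wider class than AEs requiring hospitalisation.
- **That the 7% margin is weakened.** Section 10.6 set it in advance by expert consultation, and SAE counts in this trial cannot change it.

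The primary endpoint, alpha and power are untouched.

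**What to change.** 1. **Section 8.6.3:** replace the single D15 reference with a rule tied to section 8.1. Prolongation would mean a stay of more than 24 hours beyond the planned discharge of the patient's own arm. State the arm 3 discharge day explicitly, since D17 and D18 are both readable from the present text. Say also whether the planned-stay exemption covers an AE that needs in-patient care during the planned stay.
2. **Re-check** SAEs already reported as serious only by prolongation. Apply the same check in all arms, masked to arm where possible. An unmasked re-review of arm 3 alone would introduce a one-sided reclassification.
3. **Reporting:** give SAE frequency with and without prolongation-only events, using the seriousness criterion already collected under section 8.6.7. This is needed because the corrected rule gives arm 3 a longer period in which the prolongation criterion cannot be met. Readmissions in arms 1 and 2 between D15 and the arm 3 cut-off should be listed beside the table, since they count by the admission criterion.

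**Cost:** one or two sentences in the protocol, a short re-check and one extra table. A few SAEs may be reclassified as non-serious. No visit, sample or treatment changes.
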